## 5.7 Variables

This study aims to include as many dietary characteristics at baseline and follow-up as realistically possible. The variables considered essential are described below.

### 5.7.1 Main Variables

Eating patterns and dietary information collected using the following questionnaires:

- Semi-quantitative food frequency questionnaire (FFQ) validated in the Spanish population (20). This questionnaire consists of 137 items. They collect the average food intake over the past year. Food consumption frequencies are recorded in nine levels (never or mostly never, 1-3 times/month, 1 time/week, 2-4 times/week, 5-6 times/week, 1 time/day, 2-3 times/day, 4-6 times/day, and more than 6 times/day). Food consumption frequencies will be calculated as the number of meals per day and multiplied by the weight of the portion sizes indicated in the questionnaire. Nutrient intake will be adjusted for energy intake. In addition, participants who have not made any changes to their dietary habits during the past year prior to the study will be asked at the first visit. Nutritional data will be extracted using the Spanish Food Composition Database (BEDCA), developed by the RedBEDCA and the Spanish Agency for Food Safety and Nutrition (21).  
(An English version is attached at the end of this protocol).
- Mediterranean Diet Adherence Index (aMED) to assess the degree of adherence to the Mediterranean Diet. Based on the Mediterranean Diet Scale (22), which includes the intake of vegetables, legumes, fruits, nuts, grains, red and processed meats, fish, the ratio of monounsaturated/saturated fats, and alcohol; the scoring scale ranges from 0 to 9 points.
- Healthy Eating Index (aHEI), based on the American Dietary Guidelines and the Healthy Eating Pyramid (23), which contains 9 items related to healthy food intake, with a maximum score of 87.5.
- Mediterranean Diet Adherence Screener (MEDAS): The MEDAS (Mediterranean Diet Adherence Screener) is a tool used to assess the degree of adherence to the Mediterranean Diet. It consists of 14 questions that explore different aspects of the characteristic dietary pattern of this diet (24). Each question is assigned a value depending on the frequency or quantity of consumption reported. The total score of the MEDAS questionnaire can range from 0 to 14 points, where a higher score indicates greater adherence to the Mediterranean Diet. This questionnaire provides an overview of an individual's dietary pattern and its alignment with the principles of the Mediterranean diet.

Physical Activity Log:

- International Physical Activity Questionnaire (IPAQ) validated in Spanish (25). Physical activity will be classified as low, medium, and high, based on the estimated energy expenditure for each activity. Activities with a metabolic equivalent task (MET) of 8 METs will be classified as vigorous; moderate activities with an energy expenditure of 4 METs; and light activities with 3.3 METs, such as walking, will be classified as sedentary or active if study participants engage in moderate physical activity for at least 30 minutes per day.

Parental Stress:

- Pediatric Inventory for Parents (PIP) (26): This is a questionnaire comprising 42 items, grouped into four domains or subscales. The purpose of the questionnaire is to measure the stress levels experienced by parents or caregivers of children with chronic illnesses. This questionnaire is scored on a Likert scale ranging from 1 (never/not at all) to 5 (always/extremely). Higher scores indicate higher stress levels.

- The Hospital Anxiety and Depression Scale (HADS) (27) is a questionnaire that detects emotional stress in non-psychiatric patients in a hospital setting. The questionnaire has been previously used in several studies to measure the emotional stress levels of parents or caregivers of children with type 1 diabetes. This questionnaire consists of 14 items grouped into two subscales, one for anxiety and one for depression. Responses are scored on a Likert scale ranging from 0 to 4 points.

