### 4.3 Secondary objectives:

\*Due to the timeliness of the study, we also proposed:

- To characterize changes in the dietary patterns of parents or guardians of patients with T1D during follow-up (6 months after diagnosis).
- To determine, using a questionnaire, changes in the physical activity of the adult subjects in the study at 6 and 12 months.
- To determine, using a questionnaire, the emotional stress produced by the diagnosis and treatment of T1D in the adult parents or guardians belonging to the families of the incident case at 6 and 12 months.
- To determine, using a questionnaire, the level of anxiety and depression produced by the diagnosis and treatment of T1D in the adults in the families at 6 and 12 months.

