## 5. METHODS

### 5.1 Study Design

This study will be a prospective, multicenter, observational study. The study will be conducted within the Pediatrics Department of the Hospital de la Santa Creu i de Sant Pau (HSCSP) (Barcelona) and the Hospital Universitari Arnau de Vilanova (HUAV) (Lleida). This study will be launched at the participating centers once a favorable opinion has been obtained from the Research Ethics Committee, and in accordance with the legislative requirements for this type of observational study.

The study design includes an initial visit that will coincide with the patient's inclusion in the study. Prior to the inclusion visit, a pre-screening period is planned. During this period, the potential candidate and their family will be invited, all study procedures will be explained and clarified, the selection criteria will be verified, and the inclusion visit will be scheduled. A follow-up visit will be conducted at 6 months throughout the study. A final visit will be conducted 12 months after enrollment (with a 1-month window).

Adult subjects from 26 households of patients recently diagnosed with T1D are planned to be included.

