#### *5.6.2 Inclusion*

Each participant invited to participate will be informed about the study both verbally and in writing, using language adapted to their understanding. Participants will be provided with a document called the "Patient Information Sheet" containing all the information of the study, adapted to a simple comprehensive level. No participant will be included until they have been duly informed by the researcher and have freely given their informed consent to participate in the study. Once compliance with all selection criteria has been confirmed and informed consent has been given, data collection will begin by completing an electronic data collection form (EDC), which will record the information available in the patient's medical history or obtained during the inclusion visit.

The inclusion visit will take place within the first week after a family member's T1D diagnosis. This will prevent any lifestyle and dietary changes from being made to the family environment.

The initial clinical evaluation of all included subjects will be performed during the study inclusion visit. Clinical and sociodemographic variables related to the participant (will be collected using an ad-hoc questionnaire and a physical examination. The variables to be collected are defined in **Table 1**. Diet and intake patterns will be collected using questionnaires related to lifestyle and dietary patterns.

These variables will be collected at the inclusion visit, the 6-month follow-up, and at the end of the study at 12 months.

**Table 1.** Study variables

| Variable                            | Source        | Value  |
|-------------------------------------|---------------|--|
| Sociodemographic variables   |               |  |
| Date of birth                       | Questionnaire | dd/mm/yyyy   |
| Age                                 | Questionnaire | Years  |
| Sex                                 | Questionnaire | Male / Female / Other / N/A                                    |
| Gender identity                     | Questionnaire | Male / Female / Other / N/A                                    |
| Area                                | Questionnaire | —  |
| Parents' education level            | Questionnaire | No education / Secondary / Vocational training / University    |
| Family variables             |               |  |
| Number of people in the household   | Questionnaire | Number   |

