### 6.2 Source of Information

In all cases, the source of information will be that obtained through the diet and physical activity questionnaires and through the physical examination of parents/guardians during the visits according to the schedule on **Table 2**. All information will be recorded in the EDC.

**Table 2.** Data collection schedule during the study

|                      | Inclusion | Basal (t= 0) | Follow-up (6 months) | Final (12 months) |
|----------------------|-----------|--------------|----------------------|-------------------|
| Informed consent     | X         |              |                      |                   |
| Physical exploration |           | X            | X                    | X                 |
| FFQ                  |           | X            | X                    | X                 |
| MEDAS                |           | X            | X                    | X                 |
| IPAQ                 |           | X            | X                    | X                 |
| PIP                  |           | X            | X                    | X                 |
| HADS                 |           | X            | X                    | X                 |

FFQ, Semi-quantitative food frequency questionnaire; MEDAS, Mediterranean Diet Adherence Screener; IPAQ, International Physical Activity Questionnaire; PIP, Pediatric Inventory for Parents; HADS, Hospital Anxiety and Depression Scale.

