### 6.3 Data Analysis

Data validation and quality control will first be performed through a descriptive analysis, expressing frequencies and extreme values for all recorded variables. Any errors detected will be corrected through a search for and recovery of missing data and an analysis of inconsistencies. Subsequently, a description of the sample will be provided, expressing the frequency distribution of the qualitative variables, and the arithmetic mean, median, and standard deviation, as well as maximum and minimum values for the quantitative variables.

The main analysis will consist of estimating the frequency and/or mean of post-treatment changes (reduction/increase). A paired data analysis of the changes will also be performed. A mixed-effects analysis (linear link GLM) will be performed for continuous variables. This same analysis will be performed for other dichotomous efficacy variables (improvement or lack thereof in each parameter) using logistic link GLM models. In addition, for the comparative analysis from time 0 to 6 months, parametric and nonparametric comparison tests (Student's t-test, chi-square, Wilcoxon test) and linear regressions will be applied to observe the influence between variables, taking into account the follow-up time. Family units will be phenotyped based on their variables by creating clusters using the k-means algorithm.

In all analyses, a type I error or  $\alpha$  of 5% will be established, with statistical significance when p values are less than 0.05, and a type  $\beta$  error of 20% (statistical power of 80%). Statistical analyses will be performed using the R Core Team statistical package (2023) v. 4.3.

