## **8. WORK PLAN (tasks, milestones, and study timeline)**

This project is divided into phases:

*Phase 1 (April 2024 - April 2026): Recruitment.*

Recruitment will begin in February, the expected date for obtaining the IRB documentation from each center. This period will last two years.

*Phase 2 (April 2024 - April 2026): First visit.*

Once the participants have been recruited and have signed the IRB, their first visit will include completing the questionnaires, interview, and physical examination. This first visit will take place no more than one week after the child's T1D diagnosis.

*Phase 3 (September 2024 - September 2026): Follow-up.*

The follow-up visit will take place 6 months after the first visit. The questionnaires, interview, and physical examination will be repeated.

*Phase 4 (April 2025 - April 2027): Final visit.*

The final visit will be conducted 12 months after the first visit. The questionnaires, interview, and physical examination will be repeated.

*Phase 5 (September 2026 - April 2027): Data analysis.*

In the final part of the study, the data of the patients who completed the final visit will be analyzed. This will begin with database cleaning and management, analysis, and subsequent interpretation and discussion of the results.

*Phase 6 (April 2027): Study closure.*

Once all final visits are completed, data analysis will be finalized, and communications and manuscripts will be prepared. A research meeting will be held to prepare the final report and close the study.

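### The past-year food frequency questionnaire is repeated 6 months after diagnosis, so about half of its window is pre-diagnosis diet, and a sustained early dietary change will be understated

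*Protocol*

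**What the plan says.** Section 5.7.1 of the protocol describes the FFQ as a validated 137-item form and says of its items: "They collect the average food intake over the past year". No other recall period is given for it anywhere, and the English form in section 14 prints none.

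On timing, section 5.6.2 states: "The inclusion visit will take place within the first week after a family member's T1D diagnosis". Table 2 in section 6.2 schedules the FFQ at baseline, 6 months and 12 months. Section 8, Phase 3, confirms that the same instruments are used: "The follow-up visit will take place 6 months after the first visit. The questionnaires, interview, and physical examination will be repeated".

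The 6-month result is used. Section 4.3 makes dietary change at 6 months a secondary objective. Section 6.3 plans, "for the comparative analysis from time 0 to 6 months, parametric and nonparametric comparison tests", without naming the instruments to be compared. It also says: "A mixed-effects analysis (linear link GLM) will be performed for continuous variables", without saying how time enters that model. The limitations in section 6.5 do not mention recall.

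**The concern.** The one-week limit on the inclusion visit exists to keep the baseline free of diet changed by the diagnosis. Section 5.7.1 supports this by asking, at the first visit, about dietary changes in the preceding year. Nothing comparable protects the 6-month measurement, although the study's hypothesis is that diet changes soon after diagnosis. A past-year questionnaire given then mixes old and new diet in a single answer.

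Three things are at stake:

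- A small or null 6-month FFQ result could be read as no early change when it partly reflects the recall window.
- The FFQ and MEDAS could disagree at 6 months for a reason unrelated to diet.
- The course over time, which the principal aim in section 1 sets out to evaluate, could be distorted. An early change that was simply maintained would appear to keep growing up to month 12.

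**Working it through.** **Inputs.** FFQ recall is 12 months (5.7.1). Baseline is at most 7 days after diagnosis (5.6.2). Follow-up FFQs are at 6 and 12 months (6.2, 8), and the final visit has a 1-month window (5.1). The protocol gives no dietary trajectory and no recall weights, so those below are assumptions. It states no attenuation figure to reproduce.

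**Windows, in months from diagnosis.**

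| Visit | Window | Pre-diagnosis share |
|---|---|---|
| Baseline | about −12 to 0 | at least 98% (7/365 = 2% after diagnosis) |
| Month 6 | −6 to +6 | 6/12 = 50% |
| Month 12 | 0 to +12 | 0% |
| Final visit at month 11 | −1 to +11 | 1/12 = 8.3% |

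No window is stated for the 6-month visit. If it fell at month 5 or 7, the pre-diagnosis share would be 7/12 = 58% or 5/12 = 42%.

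**Effect of the overlap.** Let F0 and F6 be the FFQ values at baseline and month 6, P the mean post-diagnosis intake, and w the recall weight on post-diagnosis months. With a stable prior diet and a score linear in intake:

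F6 = (1 − w)·F0 + w·P, so F6 − F0 = w·(P − F0).

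- Equal weighting: w = 6/12 = 0.50.
- Weight rising linearly from zero to the visit: w = (12² − 6²)/12² = 108/144 = 0.75.

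The overlap alone therefore leaves 0.50 of the mean post-diagnosis change under equal weighting, or 0.75 under this form of recency weighting.

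**Overlap separated from gradual build-up.** The table takes a true month-6 change of 1 and equal weights. The middle column is a past-6-month recall, which has no overlap.

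| Course | Past 6 months | Past year |
|---|---|---|
| Immediate change, held | 1.00 | 6/12 = 0.50 |
| 3-month build-up, then held | (1.5 + 3)/6 = 0.75 | 4.5/12 = 0.375 |
| 6-month build-up | 3/6 = 0.50 | 3/12 = 0.25 |

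In each row the overlap contributes a factor of 0.50. The rest of the shortfall is averaging of a gradual change, which any recall of that length would show.

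**Direction.** Suppose the change is complete for months 0 to 3 and fades linearly to zero at month 6. The past-year FFQ reads (3 + 1.5)/12 = 0.375 against a true month-6 change of 0. As a measure of the month-6 state, it then overstates.

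**Course from month 6 to month 12.** A change of 1 made at diagnosis and held reads 0.50 at month 6 and 1.00 at month 12. The FFQ shows a gain of 0.50 between visits that did not occur.

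**The case against.** The strongest reply is that the harm is narrow. It touches the FFQ-derived part of one secondary objective, the one-year comparison stands, and MEDAS is also given at 6 months. That is right about the extent. However, the protocol states no recall period for MEDAS, so it is not shown to be free of the same problem, and nothing gives it priority at 6 months.

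Several premises are also inferred. That aMED and aHEI are scored from the FFQ follows only from their being built on food intakes and having no row in Table 2. Section 6.3 names no instrument for the 0-to-6-month comparison. The appended FFQ prints no recall period, so the instruction actually given at month 6 is not visible. These limits stand, but the past-year recall in 5.7.1 is the only one stated.

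The matter could be left to a statistical analysis plan. Recall, however, is a property of data collection. Under the assumptions above with w = 0.50, P = 2·F6 − F0 can be computed on intakes before scoring. This is a usable sensitivity analysis, but it is noisy and depends on assumptions that the data cannot test.

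A reader might go further and infer a loss of power. Solving the paired calculation backwards from 26 units gives a standard deviation of the difference of about 1.75. Halving a 1-point aMED difference would then leave about 29% power. The documents do not support that claim: section 6.4 states no standard deviation and does not name the 6-month visit as the comparison being powered.

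A reader might also infer that the 6-month FFQ must be kept out of the mixed model. With visit as a category, the month-6 mean absorbs the attenuation. The month-6 values then reach the 12-month estimate only as correlated information on participants without a 12-month FFQ. Excluding them would discard data in a small study.

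**Conclusion.** The point holds for the 6-month FFQ. About half of that window is pre-diagnosis diet already counted at baseline, and the protocol neither shortens the recall nor acknowledges the overlap. For a change sustained or growing to month 6, the FFQ-derived 0-to-6-month change is biased toward no change. This includes aMED and aHEI if they are scored from the FFQ.

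The overlap alone halves the change under equal recall weighting, a stable prior diet and a score linear in intake. Linearity is doubtful for an index such as aMED, scored 0 to 9, and respondents may weight recent months more heavily, so the true size is unknown. Two stronger readings are not supported: that the bias always runs toward no change, since a fading change can reverse it, and that overlap alone leaves only a quarter of the change, since that figure also contains gradual build-up.

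The one-year primary comparison is essentially free of overlap, at most about 8% if the final visit is a month early. The point should be fixed, but it does not threaten the primary objective.

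**What to change.** 1. In 5.7.1 and 6.3, name MEDAS as the main dietary measure for the 6-month objective, after confirming that the recall period on the form in use is no longer than 6 months. State that period in the protocol.
2. Treat change from baseline to 12 months as the FFQ, aMED and aHEI result. Either drop the 0-to-6-month FFQ-derived change or report it as affected by overlapping recall, optionally with 2·F6 − F0 on intakes as a sensitivity analysis under stated assumptions.
3. In the mixed model, enter visit as a category, so that the month-6 FFQ value does not shape the 12-month estimate through a linear time trend. Keep the month-6 data in the model.
4. Add the overlap, including the apparent improvement from month 6 to month 12, to section 6.5.

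The cost is a few sentences and the written amendment that section 12 requires, with no added visit. MEDAS is a 14-item screener, so there would be no clean nutrient-level result at 6 months. If a recall period has to be added to MEDAS mid-study, the form changes and the version each participant completed must be recorded. Section 8 has 6-month visits starting in September 2024, so some may already have taken place. If the MEDAS recall is as short as one month, up to 7/30 = 23% of the baseline window could fall after diagnosis unless the form asks about the time before it.

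A past-6-month FFQ at month 6 would remove the overlap, but it would not match the baseline frame, would be more seasonal and would depart from the past-year form that section 5.7.1 describes. It is the costlier choice.

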#### 5.7.2 Other relevant variables

To conduct the study and properly assess the main variables, relevant sociodemographic and clinical variables will be collected to complement the information obtained through the questionnaires (**Table 1**). These secondary variables provide us with complementary information on their lifestyle, general health status, type of family unit, and the possible effects of changing.

## 6. DATA COLLECTION AND ANALYSIS

### 6.1 Data Collection Schedule

The study period is estimated to be 3 years (from April 2024 to February 2027). However, these times may be modified due to the administrative process for launching the study.

### 6.2 Source of Information

In all cases, the source of information will be that obtained through the diet and physical activity questionnaires and through the physical examination of parents/guardians during the visits according to the schedule on **Table 2**. All information will be recorded in the EDC.

**Table 2.** Data collection schedule during the study

|                      | Inclusion | Basal (t= 0) | Follow-up (6 months) | Final (12 months) |
|----------------------|-----------|--------------|----------------------|-------------------|
| Informed consent     | X         |              |                      |                   |
| Physical exploration |           | X            | X                    | X                 |
| FFQ                  |           | X            | X                    | X                 |
| MEDAS                |           | X            | X                    | X                 |
| IPAQ                 |           | X            | X                    | X                 |
| PIP                  |           | X            | X                    | X                 |
| HADS                 |           | X            | X                    | X                 |

FFQ, Semi-quantitative food frequency questionnaire; MEDAS, Mediterranean Diet Adherence Screener; IPAQ, International Physical Activity Questionnaire; PIP, Pediatric Inventory for Parents; HADS, Hospital Anxiety and Depression Scale.

